| Trail Making Test A and B (30) | Interval (sec), ratio (errors) | D1A, D2A, D1B, D2B | Aim 6 | Secondary outcome |
| Test of Attentional Performance (TAP) (31) | Interval, ratio (Alertness: Percentile rank of median reaction time for correct responses, percentile rank of standard deviation; Go/NoGo: Percentile rank of median reaction time for correct responses, percentile rank of standard deviation, percentile rank of errors; Divided Attention: Percentile rank of median reaction time for correct responses, percentile rank of standard deviation, percentile rank of errors, percentile rank of omissions; Visual Scanning: Percentile rank of median of critical and non-critical, respective standard deviation, omissions) | D1A, D2A, D1B, D2B | Aim 6 | Secondary outcome |
| Sleep EEG | | | | |
| First night with ≥4 hours of recording | Binary (hh:mm) | N1 | Aim 3 | Primary outcome; early termination of study participation if <4 hours |
| EEG worn for ≥4h hours in 3/3 nights | Binary (nights) | N1, N2A, N2B | Aim 3 | Primary outcome |

| | | | | |
|---|-------------------------------------|--------------------|--------------|---------------------|
| Sleep latency | Minutes | N1, N2A, N2B | Aim 4, Aim 5 | Covariate use |
| Sleep efficiency | % | N1, N2A, N2B | Aim 4, Aim 5 | Covariate use |
| Sleep spindles, slow wave sleep | Amount/hour | N1, N2A, N2B | Aim 4, Aim 5 | Primary outcome |
| Subjective tolerability of headband | Binary, nominal | N1, N2A, N2B | Aim 3 | Exploratory use |
| Actigraphy | | | | |
| Motor activity/24 hours, resting time for sleep | %, hours | N2A, D2A, N2B, D2B | Aim 7 | Exploratory outcome |
| Thresholding | | | | |
| TMS motor threshold | % MSO (maximal stimulator output) | D2A | Aim 8 | Exploratory outcome |
| tACS thresholding | mA (lower value of 21 Hz and 40 Hz) | D2A | Aim 8 | Exploratory outcome |
| Safety Monitoring | | | | |
| AEs and SAEs documentation | Events | All | All | Safety monitoring |

¹ Units of measurement or the scale.

² Occasions of evaluation or retrieval:

S = Screening

0 = Enrollment and Baseline

N1 = Night 1

D1A = Day 1 in Intervention A

N2A = Night 2 in Intervention A

D2A = Day 2 in Intervention A

PA = Phonecall in Intervention A

D1B = Day 1 in Intervention B

N2B = Night 2 in Intervention B

D2B = Day 2 in Intervention B

PB = Phonecall in Intervention B

³ The specific aims in which the variable will play a role in data analyses.

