8.1. Strategies that Apply to all the Aims

All testing described below assumes a significance threshold of $p = 0.05$. Analyses will be deemed to be statistically significant if the p-value is less than this threshold. An analysis that does not exceed this threshold will be considered inconclusive. The proposed statistical analysis strategy acknowledges that no p-value can reveal the plausibility, presence, truth, or importance of an association or effect.

There may be additional covariates included in the analysis. Data will be assessed for normality and, if deemed necessary, corrective procedures will be applied (e.g., log normalization). This correction will be applied upon consideration of the variables themselves, and not based on the result of the intended analysis.

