8.3 Aim-Specific Plans

Plans for Aim 1.

a) The proportion of participants in which stimulation and cognitive testing could be completed will be calculated after both stimulation sessions, i.e. visit 2 and visit 4 (percentage and 95% confidence interval).

Plans for Aim 2.

To evaluate the effect of gamma-tACS on cognitive testing.

a) Primary outcome: Ultra-delayed verbal memory recall (i.e. amount of words and word associations remembered the day after encoding the RAVLT) after gamma-tACS compared to after control stimulation, intra- and interindividually.

We will perform a two-way or one-way repeated measure ANCOVA with time (baseline and post-treatment) and treatment (control vs gamma-tACS) as within-subjects factors, and the order in which tACS will be applied (tACS-sham or control tACS) as covariate. Post-hoc tests will be calculated after Bonferroni correction for multiple comparisons.

Null hypothesis: There is no difference between tACS and control stimulation for ultra-delayed memory recall one day after stimulation. Alternative hypothesis: Memory recall is better after gamma-tACS than after control stimulation.

b) Secondary outcomes: Verbal and associative learning (immediate and delayed recall, recall after 5 days) and executive functions (results of Letter Fluency, Stroop Test, Trail Making Test, Tests of Attentional Performance), comparison intra- and interindividually, after gamma-tACS and control stimulation (comparison of difference

between visit 1-visit 2 and visit 3-visit 4; comparison of absolute results of visit 1 versus visit 3 and visit 2 versus visit 4; statistical tests and covariates as in a)).

Hypotheses are the same as for the primary outcome.

Plans for Aim 3.

To investigate the feasibility and adherence to wearable device (single-channel EEG during the night).

a) The proportion (percentage and 95% confidence interval) of participants with at least four hours of EEG recording in the first night.

b) The proportion (percentage and 95% confidence interval) of participants with at least four hours of recorded nocturnal data for each of all three nights.

Plans for Aim 4.

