To evaluate the effect of gamma-tACS compared to control stimulation on sleep EEG. Differences (individual level and group level, statistical tests as mentioned above) of sleep latency (minutes from lights out to sleep onset), sleep efficiency (sleep duration in relation to time spent in bed), sleep spindle frequency (maximum number per hour) and slow wave activity (maximum minutes of slow wave sleep per hour).

The statistical method will be the same as for Aim 2.

Null hypothesis: Sleep EEG does not change after gamma-tACS compared to the night after control stimulation.

Alternative hypothesis: There is a higher amount of sleep spindles and/or slow wave sleep after gamma-tACS (compared to the control).

Plans for Aim 5.

To investigate whether there is a correlation (Pearson's) between the stimulation-induced changes in cognitive testing scores and sleep EEG features after gamma-tACS versus after control stimulation (on individual and group level). This is an exploratory analysis.

Plans for Aim 6.

Comparison of cognitive test results after stimulation and sham on individual and group level using ANCOVA (see CT.gov). This is an exploratory analysis.

Plans for Aim 7. To investigate whether there is a correlation (Pearson's) between the stimulation-induced changes in motor activity features (according to the wristband accelerometer results) after stimulation in general and after gamma-tACS versus after control stimulation (on individual and group level). This is an exploratory analysis.

Plans for Aim 8.

To investigate whether there is a correlation (Pearson's) between the motor threshold (TMS) and the subjective symptoms during tACS. This is an exploratory analysis.

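### The executive and attention tests are secondary in the Aim 2 plan and Table 1 but exploratory in the Aim 6 plan, and no correction across measures is defined for them

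*Combined protocol and SAP*

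**What the plan says.** Three places in the current text assign a status to the same four instruments.

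- **Section 8.3, Plans for Aim 2, part b.** Under the secondary outcomes it lists "executive functions (results of Letter Fluency, Stroop Test, Trail Making Test, Tests of Attentional Performance". The tests and covariates are those of part a, and it adds: "Hypotheses are the same as for the primary outcome". The alternative in part a is directional and is worded for memory recall.
- **Section 4.3, Table 1.** All four instruments are tied to Aim 6 and labelled secondary, for example: "Trail Making Test A and B (30) | Interval (sec), ratio (errors) | D1A, D2A, D1B, D2B | Aim 6 | Secondary outcome". The table gives a label but no hypothesis.
- **Section 8.3, the Aim 6 plan.** It reads: "Comparison of cognitive test results after stimulation and sham on individual and group level using ANCOVA (see CT.gov). This is an exploratory analysis".

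On error control, section 8.1 sets a 0.05 threshold for all testing that follows it and states: "Analyses will be deemed to be statistically significant if the p-value is less than this threshold". It makes no exception for exploratory analyses. The only multiplicity statement is in part a of the Aim 2 plan: "Post-hoc tests will be calculated after Bonferroni correction for multiple comparisons". It may extend to part b through the instruction to use the same tests, but no family is named.

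**The concern.** There are two separate faults.

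First, the status is contradictory. Table 1 uses an exploratory label for the Aim 7 and Aim 8 outcomes, so the plan does treat secondary and exploratory as different things. An analyst could follow either passage about these four tests and claim to have kept to the plan.

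Second, whichever label applies, the plan permits an uncorrected significance claim on each of many scores. A chance result on, say, a Stroop time or a TAP score could be reported as a significant secondary finding. Section 2.2 says the study prepares a full-scale trial in mild cognitive impairment, so such a finding could carry forward.

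A smaller matter goes with these. The hypothesis carried into part b concerns better recall. It does not say which direction is favourable for completion times and errors, where lower is better, or for TAP percentile ranks. The sidedness of the tests is not stated.

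**Working it through.** **The plan's own figures.** The documents state no number of tests and no familywise error rate, so neither can be reproduced. The nearest stated figure is the sample size of 28 from dz = 0.5, power 0.80 and alpha 0.05 (section 5.1). A paired t-test with the noncentral t distribution needs 27 one-sided (power 0.825 at 28) and 34 two-sided (power 0.723 at 28). The figure therefore fits one test, one-sided, at an uncorrected 0.05.

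**Number of scores per occasion.**

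| Instrument | Section 3.6, coarse reading | Table 1, natural reading |
|---|---|---|
| Letter Fluency (correct words, perseverations, rule breaks) | 3 | 3 |
| Stroop (time, errors) | 2 | 2 |
| Trail Making (time, errors) | 2 | 4 (A and B separately) |
| TAP | 4 (one rank per subtest) | 14 = 2 + 3 + 4 + 5 |
| Total | 11 | 23 |

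The Table 1 TAP count is Alertness 2, Go/NoGo 3, Divided Attention 4, and Visual Scanning 5 (two medians, two standard deviations, omissions).

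**Number of tests.** Section 3.6 and Table 1 both give two occasions per condition: during stimulation and the day after. One gamma-versus-control comparison per score and occasion gives 11 × 2 = 22 or 23 × 2 = 46. Table 1 with Trail Making A and B pooled gives 21 × 2 = 42.

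The model is left open as a "two-way or one-way repeated measure ANCOVA with time (baseline and post-treatment) and treatment (control vs gamma-tACS) as within-subjects factors". If the two-way form is used and the occasion-specific contrasts become Bonferroni-corrected post-hoc tests, a treatment effect and a treatment-by-time effect remain for each score. That is again 2 × 11 = 22 or 2 × 23 = 46 tests at 0.05.

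**Expected false positives with no true effect** (k × 0.05, whatever the correlation):
- 22 × 0.05 = 1.1
- 42 × 0.05 = 2.1
- 46 × 0.05 = 2.3

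**Chance of at least one, if independent** (1 − 0.95^k):
- k = 22: 0.676
- k = 42: 0.884
- k = 46: 0.906

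**Chance of at least one, if correlated.** The documents give no correlation, so a range is assumed. The values come from simulating 40,000 sets of equicorrelated normal statistics.

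| k = 46, common correlation | Two-sided | One-sided |
|---|---|---|
| 0.3 | 0.79 | 0.62 |
| 0.5 | 0.60 | 0.46 |
| 0.7 | 0.39 | 0.31 |

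**Cost of correcting across everything.** One Bonferroni family of 46 gives 0.05/46 = 0.00109 per test. Power at n = 28 and dz = 0.5 is then about 0.19 two-sided or 0.26 one-sided. A correction across the whole set is therefore not practical at this sample size.

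**The case against.** The strongest reply is that this is a pilot. Section 2.2 says an effect is not required for the later trial, and section 9 rests the sample size on feasibility. Section 8.1 itself warns that no p-value shows the truth or importance of an effect, and the Aim 6 row of the aims table in section 3 already lists mean differences and regression coefficients. This limits the consequence. It does not remove the rule that labels each p below 0.05 significant, and the plan's caution about p-values favours reporting estimates.

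Several stronger readings are tempting, and the documents do not support them.

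- **At least 46 tests.** This is not a floor. It needs the Table 1 scores to be counted separately, and section 3.6 allows 22. Counting only one treatment effect per score would give 11 to 23, but part b asks for contrasts at separate visits and a two-way model adds the interaction.
- **69 tests and a 97% risk.** Part b also asks for a comparison of differences, and 23 × 3 = 69. But that contrast is the difference between the two absolute contrasts, so 69 independent tests are impossible. The visit numbers in part b also do not match section 7.1, which shows no cognitive testing at Visit 1 and only memory recall at Visit 4. The two-occasion count therefore rests on section 3.6 and Table 1.
- **A false positive is more likely than not.** This depends on the correlation. The same people repeat the same tests on consecutive days and several TAP scores come from one task, so independence is the least plausible case.
- **The label conflict causes the uncorrected threshold.** It does not. The threshold comes from section 8.1, and making the labels agree would leave it unchanged.
- **Table 1 states a directional hypothesis.** It carries a label only.
- **Bonferroni works only within one ANCOVA.** The text does not say so. What can be said is that the family is undefined and nothing is stated across measures.

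On direction, better can fairly be read as better performance. That weakens the point about times and errors but leaves sidedness and the favourable direction of each score unwritten.

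Finally, exploratory status is not the only sound choice. Part b and Table 1 both say secondary, and the version log records a decision to that effect. The Aim 6 plan also refers to a registry entry that was not available for this review.

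**Conclusion.** The point holds as two linked but separate defects: contradictory status for four instruments, and a significance rule with no defined control across their scores. The contradiction needs no assumption.

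The size depends on the reading. With 22 to 46 tests, 1.1 to 2.3 results below 0.05 are expected with no true effect. The chance of at least one is 68% to 91% under independence. For 46 tests at assumed correlations from 0.3 to 0.7 it is about 79% down to 39% two-sided, or 62% down to 31% one-sided. Even 31% is about six times the nominal 5% (0.31/0.05 = 6.2). These figures do not show that a false claim will be made, and the feasibility aims are unaffected. The text should be corrected before analysis.

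**What to change.** Give the four instruments one status in part b of the Aim 2 plan, in the Aim 6 plan and in Table 1, and deal with the 8.1 rule in the same edit.

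**Simplest route.** Remove them from part b of the Aim 2 plan and label them as exploratory outcomes in Table 1. State in the Aim 6 plan that they are reported as estimates with 95% confidence intervals, that the section 8.1 significance rule does not apply to them, and which direction of each score is favourable.

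**Alternative, if the sponsor wants them secondary.** Name a short list of measures and occasions, define that list as the family, and state a multiplicity correction across it. Give the direction and sidedness of each test, and delete the exploratory wording from the Aim 6 plan. Measures off the list would be handled as in the first route.

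In either case, check the chosen status against the registry entry that the Aim 6 plan cites.

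**Cost.** Wording in section 8.3 and Table 1; no change to visits, data collection or sample size. The downside is no significance claims on these tests under the first route, and fewer under the second.

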8.4 Planned Interim Analyses

No interim analyses will be performed.

9. Sample Size Rationale

We plan to recruit 28 healthy adults in this feasibility study (primary outcome). The sample size was computed such that the study has 95% power (alpha = 0.05) to reject the null hypothesis that 50% of the population of interest can complete the study procedures for an effect size of $g = 0.3$, meaning that if at least 80% of the study sample complete the procedures, feasibility in the population of at least 50% is established.

10. Data Capture and Database Management

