2.2. Scientific Rationale

This controlled cross-over pilot study will be used to prepare for a full-scale RCT in patients with mild cognitive impairment by investigating feasibility as well as acceptability and adherence of the study procedures in a sample of n=28 healthy elderly adults. Any effect on memory performance and sleep EEG will be documented but is not a requirement for the development of an RCT. We include people over 50 years of age because memory problems and neurodegenerative diseases (specifically Alzheimer's Disease) occur in the second half of life. The exclusion criteria are designed to ensure that people are not cognitively impaired by a disease of the brain or other impairment of bodily functions. In addition, we exclude contraindications to tACS.

The pilot study serves as a basis for the application of the technique in specific patient groups, in particular those with mild cognitive impairment.

3. Specific Aims

3.1. Aim 1

To establish acceptability of cognitive testing during tACS in healthy elderly participants. The threshold is set to 80% of participants.

3.2. Aim 2

Evaluation of an effect of a single session of gamma-tACS on memory (a) and associative memory (b) performance compared with control tACS. The estimand of interest is the comparison of the individual results of the memory tests at the individual and at the group level (paired t-test or a non-parametric test, respectively), for delayed (immediately after stimulation) and ultra-delayed recall (after a night of sleep as well as after 5 days).

3.3. Aim 3

Feasibility (a) and acceptability (b) of an ambulatory single-channel EEG device. The estimands of interest are the proportion of participants with at least four hours of recording in the first night (a) and the proportion of participants with three nights of at least 4 hours of EEG data (b).

3.4. Aim 4

The comparison of specific sleep EEG features, i.e. sleep spindles (a) and slow wave sleep (b), which are both prominently associated with cognitive functioning, especially memory processes, after each stimulation condition. Comparison will be on individual and on group level (via t-test or a non-parametric test, respectively).

3.5. Aim 5

To investigate whether there is a correlation between the effects of tACS (versus control control tACS) on memory recall and memory-associated sleep EEG features (especially amount of sleep spindles and slow wave sleep) on an exploratory level.

3.6. Aim 6

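### Section 9 powers 28 participants on a completion proportion that section 8.3 never analyses; 8.3 reports three unranked primary proportions and leaves the denominator open

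*Combined protocol and SAP*

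**What the plan says.** Section 2.2 presents the study as preparation for a full RCT through feasibility, acceptability and adherence, and sets efficacy aside: "Any effect on memory performance and sleep EEG will be documented but is not a requirement for the development of an RCT".

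Section 9 states "We plan to recruit 28 healthy adults in this feasibility study (primary outcome") and claims that "the study has 95% power (alpha = 0.05") "to reject the null hypothesis that 50% of the population of interest can complete the study procedures". The assumed difference is 0.3, so 80% against 50%. The decision rule is that "if at least 80% of the study sample complete the procedures, feasibility in the population of at least 50% is established". The term for completing the procedures is not defined there.

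Section 8.3 plans these feasibility analyses, each a percentage with a 95% CI:
- Aim 1: "The proportion of participants in which stimulation and cognitive testing could be completed will be calculated after both stimulation sessions".
- Aim 3a: the share with at least four hours of EEG on the first night.
- Aim 3b: the share of "participants with at least four hours of recorded nocturnal data for each of all three nights".

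None carries a 50% null or a test. The synopsis gives each its own 80% threshold (above 80% for Aim 1, at least 80% for 3a and 3b). Table 1 in section 4.3 marks all three as primary outcomes.

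Three other places bear on the point. Section 5.1.2 justifies the same 28 by a paired analysis (dz = 0.5, power 0.80, alpha 0.05), counts a completer as someone with Visits 1 to 7 and three EEG nights, and replaces people who drop out or have missing data. The synopsis recruits until 28 have completed everything. Section 7.5 says Visits 4 and 7 are not needed for completion, and leaves to judgement how early discontinuations enter the feasibility data.

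**The concern.** Following 8.3 to the letter never produces the result that section 9 powered. There are several candidate feasibility verdicts, no ranking, and no statement of which one supports the section 9 claim. Two separate passes, or one pass on the easiest component, could be reported as that claim.

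This matters because feasibility is what section 2.2 says the later RCT depends on. The share of people meeting two criteria can never exceed the lower of the two shares and may be well below it, so two 80% passes do not amount to 80% completing everything. The denominator is a second gap: among people selected for having completed, the completion rate says nothing.

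**Working it through.** **Inputs.** n = 28, null 0.50, alternative 0.80, alpha 0.05, power 0.95 (section 9; sidedness not stated). Thresholds of 80% (synopsis); 0.8 × 28 = 22.4, so a pass is 23/28. Enrolment ceiling 50 (section 5.1.2). The documents give no expected component rates, so those used in step 3 are assumptions.

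**1. Reproducing section 9.** Exact binomial, one-sided: the smallest k with P(X ≥ k | 28, 0.5) ≤ 0.05 is k = 19 (0.0436). Power is P(X ≥ 19 | 28, 0.8) = 0.961. No smaller n reaches 95% (n = 27 gives 0.926, n = 26 gives 0.941). A two-sided exact test would give 0.910. The intended analysis is therefore identifiable as a one-sided exact test with cut-off 19/28. The 80% rule (23/28) is stricter: P(X ≥ 23 | 28, 0.5) = 0.0005, and if the true rate is 80% it is reached with probability only 0.50. Missing the 80% rule and failing the 50% test are different events.

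**2. How far two passes can fall short.** Aim 3b implies Aim 3a, so there are two distinct criteria. Take completion to mean Aim 1 and Aim 3b together. If a and b people meet them, at least a + b − n meet both: 23 + 23 − 28 = 18, or 64.3%. P(X ≥ 18 | 28, 0.5) = 0.092, so the test does not reject. At an overlap of 19, p = 0.044 and it does. When both aims stand at 23/28, every overlap from 18 to 22 misses the 80% rule, but only 18 fails the test. At n = 50, passes of 41 and 40 leave at least 31 (62%), p = 0.059.

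**3. How often.** Exact multinomial probabilities, n = 28, with the two extremes of association considered:

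| Assumed true rates (Aim 1 / Aim 3b) | Failures | Both aims pass | Joint ≥ 23/28 | Both pass, 80% rule missed | Both pass, 50% test fails |
|---|---|---|---|---|---|
| 90% / 90% | independent | 89% | 55% | 34% | 0.3% |
| 90% / 90% | fully overlapping | 94% | 94% | 0% | 0% |
| 90% / 85% | independent | 72% | 33% | 40% | 0.5% |
| 90% / 85% | fully overlapping | 76% | 76% | 0% | 0% |

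At 80% / 80% with independent failures, the last column is 1.2%.

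**4. What the 95% power refers to.** If 80% is each component's rate and failures are independent, the joint rate is 0.8 × 0.8 = 0.64 and P(X ≥ 19 | 28, 0.64) = 0.417. The stated power needs 80% to be the joint rate.

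**5. Denominator.** Among the final 28, completion is 28/28 by construction. Among all enrolled it depends on how many were needed: 28/35 = 80% (p = 0.0003), 28/40 = 70% (p = 0.008), 28/50 = 56% (p = 0.24). The choice of denominator alone moves the verdict from certain success to no rejection.

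**The case against.** **Section 9 need not mean a composite.** It does not say that completion is Aim 1 plus Aim 3b, and its 80% matches the per-aim thresholds. Read as Aim 1 alone, any pass (23/28 or more, p = 0.0005) rejects 50% and no conflict exists. This stands as a limit on steps 2 to 4. The broad wording of section 9 and the completer definition in 5.1.2 favour the composite, but the documents do not settle it. That the verdict turns on an undefined term is part of the point.

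**The trial is not sized on feasibility alone.** A reader might infer that it is. Section 5.1.2 says otherwise, giving a paired-effect rationale for the same 28. This stands, and the two rationales need reconciling, but it does not supply the missing analysis.

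**Failures will tend to overlap.** Night 3 follows the Visit 5 stimulation, so leaving before Visit 5 fails both aims. Table 1 also lists a first night under four hours as ending participation, which would fail both. Independence is therefore towards the pessimistic end of the plausible range, and the 34% and 40% are upper markers rather than expectations.

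**Separate proportions with CIs suit a pilot.** At 23/28 the exact 95% lower limit is 63%, which already excludes 50% for that component. True, but 8.3 does not say the intervals will be read that way, and none is for overall completion.

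**Conclusion.** The point holds as a mismatch between what section 9 powers and what 8.3 analyses, made worse by an unstated denominator. That part rests on the text alone.

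The size of the possible disagreement rests on reading completion as Aim 1 plus Aim 3b, on n = 28, and on assumed rates. At 90% / 90% the aims pass while the 80% rule is missed in 0% to 34% of trials, depending on how far failures overlap.

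A reader might infer that the aims could readily pass while section 9's test against 50% fails. The numbers do not support that: it needs 18/28 or fewer completing both, and occurs in about 0.3% of trials at 90% / 90% and 1.2% at 80% / 80%, even with independent failures. Nor do the documents show that power is 42%. That figure applies only if 80% is each component's rate and failures are independent.

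This should be corrected before analysis. It does not put the sample size calculation itself in doubt, since section 9's figure reproduces.

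**What to change.** 1. Define completing the study procedures once, for use in sections 5.1.2, 7.5, 8.3 and 9: both stimulation and testing sessions completed, and at least four hours of EEG on each of the three nights. Reconcile 5.1.2 and 7.5 on whether Visits 4 and 7 count.
2. Add to 8.3, as the primary feasibility analysis, that proportion among all enrolled participants, including those replaced or discontinued, with its 95% CI and the one-sided exact binomial test against 50%. Replace the discretionary wording in 7.5 with this denominator, and state how people found ineligible after enrolling (section 5.3.2) are counted.
3. Keep Aims 1, 3a and 3b as component results with their 80% thresholds, and state that neither a single component nor separate passes establish the section 9 claim.
4. In section 9, say that the test is one-sided and that 80% is the joint rate, and distinguish the 80% rule from the test's own cut-off. Reconcile this sizing with the dz = 0.5 rationale in 5.1.2.

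The cost is wording plus one proportion from data already collected; no procedure changes. The downside is that the joint figure among all enrolled cannot exceed the component figures on the same denominator, so the headline feasibility result may be less favourable.
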